3.3.3. ED psychopathology

ED psychopathology, general psychopathology, health economic outcomes and quality of life will be measured using questionnaires. Scores for adults and adolescents are comparable for some questionnaires, e.g., the Epworth Sleepiness Scale (ESS) and the Epworth Sleepiness Scale - Child Adolescent (ESS-CHAD) but not all. If not comparable, scores will be converted into binary outcomes, e.g., scores of the Depression Anxiety Stress Scales (DASS) and Revised Children's Anxiety and Depression Scale (RCADS).

Eating Disorder Examination-Questionnaire (EDE-Q): The EDE-Q is a questionnaire assessing key behavioural features and associated psychopathology of eating disorders [49]. It includes four subscales: Restraint, weight concern, shape concern, eating concern

Revised Beliefs about Voices Questionnaire (BAVQ-R; A/a>15 years): The BAVQ-R is a self-report measure of patients' beliefs, emotions and behaviour about auditory hallucinations [50]. We have chosen this questionnaire as people with AN often report experiencing an internal voice. This so-called "anorexic voice" comments on the individual's eating, weight and shape and instructs the individual to restrict or compensate [51]. This questionnaire will provide information about patients' emotional and behavioural reactions to these auditory hallucinations. This will allow conclusions not only about the content and form, but also about the meaning given to these auditory hallucinations [50].

The Self-regulation of Eating Behaviour Questionnaire (SREBQ): The SREBQ is a self-reported measure of the patients' capacity for management of behaviour, thoughts, feelings, attention and environment in the pursuit of personal goals and measuring change in response to self-regulation interventions in adults [52]. The questionnaire will give additional information on food cravings, dietary restraint and the capacity for self-regulation in patients with AN [53].

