3.5 Secondary endpoints/outcomes

The secondary objective is feasibility (completeness and summary statistics) of recording the following measures at baseline:

Demographics and the Alcohol, Smoking and Substance Involvement Screening Test (ASSIST)

Page 25 of 60

And of the following measures at baseline (where applicable), 8 weeks, 16 weeks, 6 months, and 12 months post-baseline:

Height, weight, BMI, ED psychopathology questionnaires- (RCADS, EDE-Q, BAVQ-R, SREBQ), General psychopathology assessments and questionnaires-(DASS, RCDADS, Y-BOCS, C-SSRS), Health economic and quality of life assessments (EQ-5D-Y, CAA-SUS, , EDSIS,) olanzapine plasma levels (8 weeks only), Physical examination measures, ECG, laboratory parameters, ESS, ESS-CHAD and quality of adverse events reporting (UKU-SERS).

Also to assess willingness to participate in an RCT (blinded, placebo-controlled).

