3.6.3 Change in measures over time

Change in the measures as listed in section 3.5 will be explored/described to inform a future definitive study design.

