6.2 Exclusion criteria

Exclusion criteria:

- Serious self-harm, suicidality, psychotic disorder, serious medical comorbidities (as detailed below) which are contraindications for olanzapine
- Current alcohol or illicit drug use disorder
- On major tranquilliser or opioids
- QTc interval >450 ms (two separate ECG measurements) [47]
 - A QTc interval >500 ms in the ECG or rises by more than 60 msec from baseline or other severe cardiac side effects will stop study participation of this patient.
 - A QTc interval >500 ms in the ECG or rises by more than 60 msec from baseline or other severe cardiac side effects in more than one patient in the feasibility study will lead to a stop of the study.

Alerting liver function tests or white blood cell count [47]

- \circ Bilirubin >40 μ mol/L
- Alkaline phosphatase >200 U/L
- AST >80 U/L
- ALT >90 U/L
- GGT >90 U/L
- \circ WBC <2.0 x10⁹/L
- $\circ \quad MCV > 120 \ fL$
- On other psychopharmacological medication at stable dose for <4 weeks
- On medication interacting with olanzapine
- Pregnancy
- Of childbearing potential and unwilling to have pregnancy tests.
- Objecting to taking effective contraceptive measures as specified under section 8.10. on trial restrictions. The participant information and consent sheet include a section on pregnancy and appropriate birth control measures.
- Breast feeding
- Insufficient understanding of the Trial/lack of capacity to agree to the Trial procedures as assessed by the responsible clinician
- Hypersensitivity to Olanzapine or to any of its excipients
- Taking part in another pharmacological trial for AN
- Involvement in research that includes contraindications for treatment with olanzapine

Serious self-harm means one of the following:

• Recent (within the last 12 months) self-harm with suicidal intent

Page 29 of 60

- Recent self-harm with the risk to a person's own life (e.g., drug intake, deep cutting, burning, swallowing sharp items)
- Recent self-harm which could lead, or has led, to long lasting impairment of one's health and functioning

Serious medical comorbidities which are contraindications for olanzapine mean one of the following:

- Coronary heart disease
- Cerebrovascular disease
- Parkinson's disease, parkinsonism or dementia
- Hepatic or renal impairment

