10.3.4 Exploratory analyses

- We will also perform exploratory analyses looking at change over time in measures listed in Section 10.3.3 to inform a future definitive study design. Such analyses will use appropriate longitudinal modelling approaches; further details will be covered in the Statistical Analysis plan.
- Elements that constitute TAU will be described.
- Patient experience of recruitment and treatment, acceptability and reasons for adherence and nonadherence will be ascertained in qualitative interviews which will be performed, transcribed and analysed.

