10.7 Procedure(s) to account for missing or spurious data

The trial manager will monitor the integrity and completeness of the data weekly and approach clinical services for missing information. Trial statisticians will also monitor integrity and completeness of the data periodically and report discrepancies to the trial manager, at least prior to every DMC meeting.

We do not plan to impute or otherwise handle missing data in the analyses. Instead, missing data in this feasibility study will inform the potential application for a full RCT about risks to data completeness and integrity.

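### The BAVQ-R asks about a voice that not every patient has, but the protocol names no record of whether one is present, so not-applicable forms can pass for non-completion and voice loss can drop out of the change description

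*Protocol*

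**What the plan says.** - **What the scale measures (3.3.3).** "The BAVQ-R is a self-report measure of patients' beliefs, emotions and behaviour about auditory hallucinations [50". The reason for including it is "We have chosen this questionnaire as people with AN often report experiencing an internal voice", and its expected yield is "This questionnaire will provide information about patients' emotional and behavioural reactions to these auditory hallucinations".
- **Who receives it.** The trial summary and 3.3.3 limit it to patients over 15. The schedule in 3.7 marks it at baseline, 8 weeks, 16 weeks, 6 months and 12 months, with no condition that a voice be present.
- **Who enters the trial.** The inclusion criteria in 6.1 do not mention a voice. The exclusions in 6.2 include "Serious self-harm, suicidality, psychotic disorder, serious medical comorbidities (as detailed below) which are contraindications for olanzapine".
- **How completion is used.** A primary feasibility measure in 3.1 is the proportion of patients who complete every assessment and questionnaire at all five time points. Under 3.3.1, a questionnaire not completed in more than 25% is left out of a later pilot or full RCT application.
- **How change is used.** Section 3.5 lists "ED psychopathology questionnaires- (RCADS, EDE-Q, BAVQ-R, SREBQ" among the measures, and 3.6.3 says "Change in the measures as listed in section 3.5 will be explored/described to inform a future definitive study design". Section 10.3.4 adds "Such analyses will use appropriate longitudinal modelling approaches; further details will be covered in the Statistical Analysis plan".
- **Missing data (10.7).** "We do not plan to impute or otherwise handle missing data in the analyses".

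**The concern.** Every BAVQ-R item presupposes a voice. For a patient without one, the score is undefined rather than unobserved. Nothing in the protocol tells these patients, or the staff, what to do with the form, and nothing it lists would identify them afterwards.

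Three results are at stake:

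1. **Primary completion outcome.** One blank, not-applicable form turns a fully cooperative patient into a non-completer.
2. **The 25% rule.** The scale could be dropped for apparent poor acceptability when the true reason is that it did not apply.
3. **Change over time.** Loss of the voice is a plausible good outcome under an antipsychotic. If it leads to a blank form, some of the patients helped most leave the BAVQ-R summary.

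If patients without a voice answer anyway, the forms look complete but the scores have no clear meaning. Without a record of voice presence, the team cannot tell which of these happened.

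**Working it through.** The plan gives no figure on this point. Its only calculation, the margin of error for adherence in 10.1, does not bear on it.

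**Inputs**
- v = share of patients with a voice at baseline. Not in the documents; assumed 70% to 100%.
- s = share of those whose voice has stopped by a given visit. Not in the documents; assumed 0% to 30%.
- n = 55 (section 4), an upper bound because the scale is limited to patients over 15 and their number is not stated.
- Cut-off: more than 25% not completed (3.3.1). I read this as a share of patients at a visit; the protocol does not define the denominator.

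**Step 1: not-applicable share with full cooperation.** The share is 1 − v(1 − s). With n = 55, 25% is 13.75, so the rule is met at 14 or more. The last column is the binomial probability of that.

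| v | s | 1 − v(1 − s) | of 55 | P(14 or more) |
|---|---|---|---|---|
| 100% | 20% | 20% | 11.0 | 0.20 |
| 90% | 10% | 19% | 10.45 | 0.15 |
| 90% | 20% | 28% | 15.4 | 0.71 |
| 80% | 10% | 28% | 15.4 | 0.71 |
| 100% | 30% | 30% | 16.5 | 0.81 |
| 70% | 0% | 30% | 16.5 | 0.81 |

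The expected share passes the cut-off when v(1 − s) < 0.75. At v = 100% this needs s above 25%. At v = 90% it needs s above 1 − 0.75/0.90 = 16.7%. At v = 80% it needs s above 1 − 0.75/0.80 = 6.25%. Plausible inputs therefore fall on both sides.

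**Step 2: a smaller denominator.** Suppose 40 patients are over 15, 32 have a voice at baseline and 3 lose it. Then (8 + 3)/40 = 27.5% are not applicable, again above 25%.

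**Step 3: primary completion outcome.** If every not-applicable form is left blank, completion among patients over 15 cannot exceed v(1 − s). That is 72% for 80% and 10%, and 80% for 100% and 20%, with nobody uncooperative.

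**Step 4: direction of the effect on change.** Take an underlying severity in SD units with baseline/follow-up correlation r = 0.5. Let the voice stop in the share s with the lowest follow-up severity, and leave those patients out. The observed mean change is then shifted by (1 − r) × φ(z)/(1 − s), where z is the normal quantile for s. For s = 20% this is 0.5 × 0.280/0.80 = 0.175, so a true −0.50 is seen as about −0.33. Simulation gives −0.40, −0.33 and −0.25 for s = 10%, 20% and 30%. Between 61% and 66% of the patients still scored have improved. Improvement is understated, not abolished. This shows direction only; the size rests on the assumptions.

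**The case against.** - **The protocol does not say these patients become missing.** A reader might infer that every patient whose voice stops drops out of the data. That is not stated. Such a patient could disagree with every item and be scored, and the improvement would then show. This stands: missing forms are one possibility, uninterpretable answers another.
- **The remaining patients are not only those the drug failed.** A reader might infer that the change score would cover just the unhelped. Patients whose voice persists but weakens, or whose beliefs about it improve, still contribute, and Step 4 has most of them improving. This stands.
- **Scoring no voice as zero would exaggerate the effect.** It can make the gap look very large, but it gives a number to a state the scale does not measure, and the documents contain no such rule.
- **A voice item may exist.** The questionnaire form and eCRF are not shown, and 11.1 says missing-data codes are programmed into all fields. This stands in part: one can say only that the protocol mentions no voice item and no not-applicable category.
- **This is SAP material.** Denominators and change models usually are, and 10.7 does not forbid tabulating reasons for a blank. But the protocol fixes the visit schedule, the 25% rule and the completion outcome, and no SAP can recover voice presence that was never collected. Patients of 15 or under can be exempted from the counts because age is recorded; patients without a voice cannot.
- **The stakes are modest.** The study has one arm, change is exploratory, and learning that a scale does not apply to many patients is a legitimate feasibility result. True, but that result can be read only if not applicable is distinguishable from not completed.
- **Excluding psychotic disorder does not conflict with measuring an anorexic voice.** Agreed; no contradiction is claimed.

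**Conclusion.** The point holds in limited form. The BAVQ-R depends on a voice that the protocol itself does not expect in every patient, it is scheduled at every visit regardless, and the protocol names no way to identify those to whom it does not apply. Followed as written, the plan can count cooperative patients as non-completers and reject the scale for the wrong reason. It can also leave out of the change description some of the patients helped most.

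The size cannot be established. Under the assumed inputs the not-applicable share is 28% to 30% in some cases and 19% to 20% in others, either side of the 25% cut-off. These figures assume that patients without a voice leave the form blank. The documents do not support saying that voice loss must produce missing data, nor that the change score would describe only unhelped patients. Because the change analysis is exploratory, the main consequence is for the feasibility counts. The change is worth making but does not threaten the study.

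**What to change.** 1. Add one yes/no item before the BAVQ-R at every visit, asking whether the patient currently experiences such a voice.
2. Record not applicable separately from not completed.
3. For the BAVQ-R, use patients with a voice at that visit as the denominator in the 25% rule (3.3.1). In the primary completion outcome (3.1), do not count a not-applicable BAVQ-R against the patient.
4. Report the proportion with a voice at each visit among all patients over 15, alongside BAVQ-R scores in those with a voice at that visit and the number whose voice has stopped. Loss of the voice then appears as a result and not as a gap.

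The cost is one extra item per visit, a tabulation rule, and a smaller denominator for BAVQ-R scores and completeness.

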3.3.4. General psychopathology

As AN has been found to be associated with depressive disorder [4], anxiety disorders [5], OCD [6] and autism spectrum disorder [7], shows an overlap with schizophrenia on a symptomatic and genetic level [53,64], and because we are testing olanzapine, an antipsychotic drug [55], we decided to include scales measuring general psychopathology related to the mentioned disorders.

Depression Anxiety Stress Scales (DASS): The DASS [56] is a 42-item instrument designed to measure the three related negative emotional states of depression, anxiety and stress. Over 20 years, it has been vastly used in research and has been evaluated in large clinical samples to investigate symptoms of depression, anxiety and stress (e.g. [56,57]).

For adolescents, we will use the Revised Children's Anxiety and Depression Scale (RCADS): The RCADS is a 47-item questionnaire that measures the frequency of various symptoms of anxiety and low mood. This questionnaire is commonly used in studies involving adolescents. Therefore, we use it in addition to the DASS. The RCADS produces a total anxiety and low mood score, and separate scores for each of the follow sub-scales [58]: Separation anxiety, social phobia, generalised anxiety, panic, obsessive compulsive, total anxiety and low mood.

Yale-Brown Obsessive-Compulsive Scale (Y-BOCS): The Y-BOCS [59] is a clinician-administered 10item scale designed to measure the severity and type of symptoms in people with OCD. The symptoms assessed are obsessions and compulsions. The Y-BOCS is sensitive to changes in OCD symptoms. Therefore, it has been extensively used in clinical studies in over 30 years (e.g. [60,61]). The Y-BOCS version for adolescents is the Children's Yale-Brown Obsessive-Compulsive Scale (CY-BOCS).

Columbia Suicide Severity Rating Scale (C-SSRS): The C-SSRS is a suicidal ideation rating scale created to evaluate suicidality in adolescents and adults (12 years and up) [62]. It rates an individual's degree of suicidal ideation and has been used successfully in research in adolescent as well as adult populations (e.g. [63,64]).

3.3.5. Health economic and quality of life assessment

EQ-5DTM: The EQ-5D is a standardized instrument developed by the EuroQol Group as a measure of health-related quality of life that can be used in a wide range of health conditions and treatments. It consists of a descriptive system, which comprises five dimensions: Mobility, self-care, usual activities, pain/discomfort and anxiety/depression. In the 30 years since its development, it has been successfully used in several thousand national and international studies (e.g. [65,66,67] to measure quality of life. EQ-5D-Y, a version adapted for youths will be used for the OPEN study [67].

Page 23 of 60

Adult Service Use Schedule (AD-SUS): The AD-SUS has been developed and employed in several mental health trials (such as [68]) Information about the study participants' use of services will be collected in interviews with a researcher at baseline, at 6- and the 12-month follow-ups. At baseline, information will cover the previous 3 months. At each of the follow-up interviews, service use since the previous interview will be recorded; in this way, the entire period from baseline to the final follow-up will be covered. The AD-SUS contains a researcher- and a self-completed section. Both sections together will cover: The number and duration of contacts with various services and professionals, the use of psychological therapies, and the use of non-trial pharmacological therapies including sleeping tablets, mood stabilisers and painkillers. In the OPEN study, the Child and Adolescent and Adult Service Use Schedule (CAA-SUS) will be used. The CAA-SUS a questionnaire designed specifically for the OPEN study, which incorporates features of CA-SUS and AD-SUS will be applied to take the health and social care perspective.

Eating Disorders Symptom Impact Scale (EDSIS): The EDSIS has been developed as a measure to assess the specific caregiving burden of both AN and bulimia nervosa [69]. Subscales of the EDSIS are related to: Nutrition, dysregulated behaviour, guilt and social isolation.

3.3.6. Drug adherence measures

Olanzapine plasma level: We will perform therapeutic drug monitoring and measure olanzapine levels at week 8 after the start of olanzapine treatment. [70]. An independent physician will have immediate access to olanzapine levels, and feedback to the study team if the level exceeds the upper normal limit. Pill count: We will use the pill count as an indirect measure of adherence. Thus, the number of dosage units that have been taken/not taken will be counted. We are, however, aware that the removal of a dosage unit does not mean that the medication has been taken, that it does not characterize the adherence pattern, and that it is unable to identify causes of adherence or non-adherence. Therefore, we will use pill count in addition to the olanzapine plasma level [71].

3.3.7. Drug safety measures

Adverse effects: In OPEN, we will measure possible adverse effects in a structured and standardised manner. As there are no existing guidelines concerning the use of antipsychotics in AN, we decided on the clinical outcome measures of adverse effects based on the World Federation of Societies of Biological Psychiatry (WFSBP) Guidelines for Biological Treatment of Schizophrenia [72].

- Physical examination:
 - Weight
 - Blood pressure (BP) and pulse
 - Body temperature
- Electrocardiogram (ECG): A QTc interval of > 450 ms confirmed by a second ECG measurement or an otherwise seriously abnormal ECG [47] will be an exclusion criterion for this study. We will only exclude patients if two separate readings are >450ms.
- A QTc interval >500 ms in the ECG or rises by more than 60 msec from baseline or other severe cardiac side effects will stop study participation of this patient.
- A QTc interval >500 ms in the ECG or rises by more than 60 msec from baseline or other severe cardiac side effects in more than one patient in the feasibility study will lead to a stop of the study after the feasibility phase.
- Laboratory parameters: Routine laboratory parameters in patients with AN often show alterations, including electrolytes, liver enzymes, kidney parameters, leukocyte count, haemoglobin and others. Additionally, medical problems secondary to AN, or due to the treatment itself may lead to further laboratory abnormalities [10]. Furthermore, olanzapine may lead to changes in metabolic parameters, including cholesterol, plasma glucose and blood fats [73]. Therefore, the following parameters will

Page 24 of 60

be determined at baseline, 8 weeks, 16 weeks (end of trial medication) and at the 12-month followup.

- Electrolytes and salt/water balance
- Kidney function
- Liver function
- Blood count/bone marrow
- Plasma glucose (fasting or random) or glycated hemoglobin (HbA1c) and lipid profile
- Pregnancy test in women and female adolescents
- UKU-Side Effect Rating Scale (UKU-SERS): The UKU-SERS [74] is a general rating scale for the registration of unwanted side effects of psychotropic medication. UKU is an acronym for the Danish name "Udvalg for Kliniske Undersøgelser" (Task force for clinical investigations). UKU was a task force of the Scandinavian College of Neuropsychopharmacology (SCNP) working with the development of rating scales and methodological issues in relation to psychopharmacological research. It covers a broad range of different possible side effects and has been widely used in clinical studies since its development and publication in 1987 (e.g. [75,76].
- Epworth Sleepiness Scale (ESS): The ESS is a self-administered questionnaire that provides a measurement of the general level of daytime sleepiness [77]. Since its development, it has been used in several thousand clinical studies (e.g. [78-79]). Sleepiness is a frequent symptom in patients with AN, because starvation results in a fragmentation of sleep and a reduction of slow wave sleep, and thus abnormalities in sleep efficiency and sleep architecture [80,81]. On the one hand, daytime sleepiness is a common side effect of antipsychotics, and specifically olanzapine is known to induce moderate somnolence [82], on the other hand, it has been shown to lead to an improvement of sleep [37] and may thus reduce AN-associated daytime sleepiness.

Table 1 provides a synopsis and schedule of all assessment tools used in OPEN. We have listed many outcome parameters. However, given the multiple comorbidities of AN which were explicitly mentioned in the HTA call 16/97 and the number of potential side effects of olanzapine [55], this multitude of parameters makes sense from a clinical perspective.

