One reason for the NIHR HTA call for a study testing antipsychotics in young people with eating disorders is the discrepancy between EDs treatment guidelines and clinical practice. Whereas treatment guidelines such as NICE do not recommend psychopharmacological treatment, between 80% and 90% of patients with EDs are taking psychopharmacological drugs. Instead of taking medications without EDs indication and without monitoring, this open-label feasibility study will test olanzapine in a well-defined patient group. Olanzapine is a medication approved for the treatment of schizophrenia, and its risk profile is well-known. However, if olanzapine is added to psychotherapy, it might lead to a slightly increased risk of adverse events.

Despite being licensed for Schizophrenia, Olanzapine is already in use in patients with treatment-resistant anorexia nervosa [43], it has been tested successfully in randomized-controlled trials [30], and it is

Page 20 of 60

recommended for weight gain in people with anorexia nervosa with category grade B evidence by the WFSBP guidelines on the pharmacological treatment of eating disorders World Federation of Societies of Biological Psychiatry (WFSBP) guidelines for the pharmacological treatment of eating disorders [98]. We will manage the risk by excluding patients with a specifically high risk. People with pregnancy, women of child bearing potential not willing to do a pregnancy test and not willing to adhere to contraceptive measures as specified under section 8.10 (Trial restrictions), people with serious self-harm, suicidality, psychotic disorder, serious medical comorbidities which are contraindications for olanzapine, current alcohol or illicit drug use disorder, on major tranquilliser or opioids, QTc interval >450 ms (two ECG measurements), alerting liver function tests or white cell count [47], on other medication at stable dose for <4 weeks, on medication interacting with olanzapine are considered as high risk. We will use appropriate guidance and instructions for QTc measurement in the same standardised way throughout the trial. The instructions will cover things like the same level of activity before ECG measurements (e.g., sitting or lying after two minutes rested), that if both readings are significantly different, then rather than take an average, redo with a different machine. We will also take consideration of factors such as age, gender, potassium levels, family history, and cardiac examination results.

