We will examine and document all physical and mental comorbidities that are not exclusion criteria. For example, mood disorders, obsessive-compulsive disorder, anxiety disorders and personality disorders are common co-morbidities which are not exclusion criteria.

In order to determine inclusion and exclusion criteria, to detect serious physical or mental illnesses, and to find out current medications or potentially needed medication, a full psychiatric and medical history taking, physical examination and assessment will take place when screening potential participants, including:

- Body weight and height
- Blood pressure and pulse rate, lying and standing
- Body temperature
- Muscle strength
- Skin
- Signs of infection and nutritional deficiency
- Alcohol, Smoking and Substance Involvement Screening Test (ASSIST) for study participants >15 years old; all participants will be screened for alerting levels of GGT and MCV as indicators of alcohol use; alcohol and drug use is a health risk for people on olanzapine [85]

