7.1.2 Screening

The aim of the screening process is to ascertain whether inclusion and exclusion criteria are met. In accordance with the inclusion and exclusion criteria outlined in section 6.1. and 6.2., the clinical research team will update the eCRF with the following information about the potential participant after informed consent is obtained:

- Age
- Gender
- Diagnosis of AN
- Level of nonresponse to TAU (at least one month of treatment; weight gain <2 kg within at least one month of TAU; outpatients should have attended ≥4 therapeutic sessions.
- Potential serious self-harm, suicidality, psychotic disorder
- Serious medical comorbidities which are contraindications for olanzapine
- Current alcohol or illicit drug use disorder
- Use of major tranquilliser or opioids
- QTc time
- Liver function tests or white cell count
- Use of other medication at stable dose for <4 weeks
- Use of medication potentially interacting with olanzapine
- Pregnancy test, willingness to take further pregnancy tests after 8 weeks, 16 weeks, 6 months, and 12 months and to take contraceptive measures as specified in section 8.10. on trial restrictions (females of childbearing potential only)
- Breast feeding
- Capacity of the adult participant or the adolescent participant and their legal representatives to agree to the study

For definition of serious self-harm and serious medical comorbidities see section 6.1. and 6.2.

To obtain this information and thus determine inclusion and exclusion criteria, a full psychiatric and medical history taking, physical examination and assessment will take place. See section 6.1. and 6.2. To obtain this information is included in the standard care for a patient with AN if pharmacological treatment is considered.

Page 31 of 60

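### Section 3.3.7 names a serious non-QTc ECG abnormality as an exclusion, but its next sentence and the operative list in 6.2 allow exclusion on QTc only

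*Protocol*

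**What the plan says.** Four places in the protocol bear on the ECG as an entry criterion.

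- **Section 3.3.7 (drug safety measures), first sentence of the ECG bullet.** There are two grounds joined by 'or': a QTc above 450 ms confirmed on a second ECG, and "an otherwise seriously abnormal ECG [47] will be an exclusion criterion for this study".
- **Section 3.3.7, next sentence.** "We will only exclude patients if two separate readings are >450ms".
- **Section 6.2 (exclusion criteria).** The ECG entry reads "QTc interval >450 ms (two separate ECG measurements) [47]". Its two sub-bullets (QTc above 500 ms, a rise of more than 60 msec from baseline, or other severe cardiac side effects) stop a patient's participation or the study once treatment has begun. They are not entry rules.
- **Section 7.1.2 (screening).** The eCRF is completed "In accordance with the inclusion and exclusion criteria outlined in section 6.1. and 6.2", and the only ECG item in its list is the QTc time.

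Section 2.4 also lists high-risk patients to be excluded, with "QTc interval >450 ms (two ECG measurements), alerting liver function tests or white cell count [47]" among them. It adds, after its guidance on QTc measurement, "We will also take consideration of factors such as age, gender, potassium levels, family history, and cardiac examination results".

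**The concern.** Eligibility rules should give one answer for one patient. Here the answer depends on which page is read, and the page that sites are told to use has the narrower rule. Someone with a QTc below the threshold but a serious arrhythmia or conduction abnormality is barred by the first sentence of 3.3.7. Under 6.2 that finding is not an entry criterion, so the decision passes to the individual clinician.

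The subject is cardiac safety in a population as young as 12 receiving olanzapine off-label. Section 1.1 names sudden cardiac death with ventricular arrhythmias as one of the most common causes of death in anorexia nervosa. That is general background and gives no risk figure for patients with a normal QTc, but it explains why a stated ECG exclusion should not be left ambiguous.

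There is also a small reporting consequence. The numbers approached, screened and included are a main feasibility result (section 10.3.2), and the trial summary lists screen-failure information as data to be collected. If sites apply different ECG rules, ECG-related screen failures will not be classified alike.

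**Working it through.** No arithmetic applies, and the plan gives no figure to reproduce. The check is to take one hypothetical patient and apply each text in turn: QTc below 450 ms on every reading, with a serious ECG abnormality of another kind.

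| Text | Result for this patient on ECG grounds |
|---|---|
| 3.3.7, first sentence | Excluded by the second ground |
| 3.3.7, next sentence, read literally | Not excluded: two QTc readings above 450 ms are required |
| 6.2, ECG entry | Not excluded: QTc only |
| 6.2, sub-bullets | Not applicable before treatment |
| 6.2, defined comorbidities | Not excluded unless the abnormality reflects a listed disease |

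**The comorbidity route.** Section 6.2 closes this definition: "Serious medical comorbidities which are contraindications for olanzapine mean one of the following". Four entries follow: coronary heart disease; cerebrovascular disease; Parkinson's disease, parkinsonism or dementia; and hepatic or renal impairment. Coronary disease is the only cardiac entry. Arrhythmia, conduction disorder and abnormal ECG are not listed. Reading through all 15 top-level criteria in 6.2 finds no other that covers a non-QTc ECG abnormality.

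**Readings of 3.3.7.**

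1. The second sentence only explains the two-reading rule for QTc. This is the more natural reading. Section 3.3.7 then keeps two grounds against one in 6.2, and the two sections conflict.
2. The second sentence governs the whole ECG exclusion. Section 3.3.7 then agrees with 6.2 but contradicts its own preceding sentence, and the phrase about an otherwise abnormal ECG is a leftover.
3. The abnormal ECG is merely another way of confirming a raised QTc. This is strained. It would also let a single QTc reading plus an abnormal tracing exclude a patient, which differs from the two-reading rule in 6.2 and 2.4.

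Each reading leaves something to correct.

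**Sections 2.4 and 7.1.2.** Neither contains the second ground, but neither fully copies 6.2. Section 2.4 omits breast feeding, hypersensitivity, capacity and participation in another trial; 7.1.2 omits hypersensitivity and participation in another trial. Their silence is weak evidence. The comparison that carries the point is one phrase in 3.3.7 against one line in 6.2. Section 7.1.2 matters mainly because it makes 6.1 and 6.2 the working list.

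The QTc threshold itself, above 450 ms on two measurements, is the same in 2.4, 3.3.7 and 6.2 and is not in question.

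**The case against.** The strongest reply is that the protocol already settles on one rule. Because of the word 'only', the second sentence of 3.3.7 ends at the same QTc-only rule as 6.2, 2.4 and 7.1.2, and what remains is a stray phrase in a section on outcome measures. The amendment history can be cited in support: version 1.1 clarified the eligibility criteria, partly for consistency with the electronic data capture system, so the wording of 6.2 may be the considered one. This stands in part. It shows that the direction of the error is open, but it does not remove the error, because 3.3.7 still declares an exclusion that 6.2 lacks.

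The second reply is that little would happen in practice. Sections 3.7 and 7.6.1 provide for an ECG at screening. A full history and physical examination is required, among other aims "to detect serious physical or mental illnesses". Section 2.4 considers cardiac examination results, section 8.3 applies BNF standards, and section 7.10 lets the physician withdraw a patient for medical reasons and stops olanzapine for severe cardiac problems. All of this stands and lowers the risk. None of it makes a serious non-QTc abnormality an entry exclusion.

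A reader might go further and infer that screening looks at nothing on the ECG but QTc, so that such abnormalities would pass unseen. The documents do not support that: the QTc-only entry is true of the 7.1.2 list, while 7.6.1 includes the ECG among the screening data entered in the database.

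**Conclusion.** The inconsistency is real, of minor to moderate severity. Section 3.3.7 states an ECG exclusion that its own next sentence appears to withdraw and that the operative list in 6.2 does not contain. A patient with a normal QTc and another serious ECG abnormality is excluded by one text and eligible on ECG grounds by the other.

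A reader might infer that 6.2 has lost an exclusion the sponsor definitely wanted, or that a known number of at-risk patients would be enrolled. Neither follows. Nothing in the protocol shows which wording is intended, and it gives no frequency of seriously abnormal ECG with normal QTc, so the number affected cannot be estimated.

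There is no effect on the sample size of 55 or on the analysis, other than how ECG-related screen failures are classified. The conclusion rests on the text alone. It assumes that sites work from 6.2, as 7.1.2 directs.

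**What to change.** Align the two texts, preferably in the safer direction.

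1. In 6.2, extend the ECG entry with: *or an otherwise seriously abnormal ECG, as judged clinically significant by the responsible physician*.
2. Add a matching item to the screening list in 7.1.2.
3. Begin the second sentence of the ECG bullet in 3.3.7 with *For QTc,* so that it no longer reads as cancelling the other ground.

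Reference 47 is cited beside this exclusion in 3.3.7, and section 10.3.3 relies on it for concerning and alerting ECG parameters. The protocol does not show that it defines a seriously abnormal ECG, so check it before using it as the definition.

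If the sponsor does not intend this exclusion, delete the phrase from 3.3.7 instead. That also resolves the conflict.

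The cost of the preferred route is a wording amendment and one eCRF item. No new procedure is needed, because the ECG is already done at screening. The downsides are possibly a few more screen failures and some variation between sites in clinical judgement.
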